### 2.2.3 Pediatric Clinical Trials

No pediatric studies of INCB007839 have been conducted to date.

### 2.3 Rationale for proposed pediatric study

Pediatric patients with recurrent/progressive high-grade gliomas have a very poor prognosis. Therapeutic agents to date have had limited success when targeting mechanisms intrinsic to the glioma cell. The use of an ADAM10 inhibitor like INCB007839 is a promising therapeutic strategy to target elements of the tumor microenvironment that promote glioma progression, and therefore represents a novel therapeutic strategy.

Overall, INCB007839 is a safe and tolerable drug in adult patients with advanced cancer. In addition, the preclinical data described above suggests that INCB007839 inhibits growth in pediatric high-grade gliomas and DIPG. This study will allow a more detailed description of the safety and tolerability of INCB007839 in pediatric patients with recurrent/progressive high-grade gliomas and also obtain preliminary data regarding the efficacy of this treatment approach.

Given that the adult recommended phase 2 (RP2D) dose of INCB007839 SR was 200 mg BID, we propose to test the safety and tolerability of pediatric equivalent dose based on a typical adult size of 1.67 m^2: 120 mg/m^2. Thus, this clinical trial will start at 120 mg/m^2 and de-escalate to 80 mg/m^2 if the former is not tolerable. INCB007839 SR will be administered orally, twice a day each day for 28-day cycles. Treatment may continue up to 26 courses (2 years) in the absence of disease progression or unacceptable toxicity.

Limited preclinical data suggest that ADAM10 deletion may be associated with abnormal bone growth; the potential effect of INCB007839 on bone development will therefore be monitored in this study by knee X-rays (that capture the tibial growth plate), and knee MRI if clinically indicated.

## 2.4 Correlative Studies Background

### 2.4.1 Rationale for Pharmacokinetic Studies

#### 2.4.1.1 *Hypothesis*

The pharmacokinetics and tolerability of INCB007839 in pediatric patients with recurrent/progressive high-grade glioma will be similar as compared to prior studies of INCB007839 in the adult population.

#### 2.4.1.2 *Preclinical and Clinical Data*

Pharmacokinetic studies will be essential for evaluating and interpreting toxicity and outcomes as there are no previous pediatric studies with INCB007839. Though it is hypothesized that the pharmacokinetics and tolerability will be similar between pediatrics and adults, there may be differences based on patients' previous treatment, age, weight, body habitus, and other co-factors. Additionally, evaluating plasma  $C_{max}$  and AUC and comparing to preclinical animal models will aid in understanding lack of efficacy, if present. Pharmacokinetic studies will be assessed pre-treatment and post-treatment during Course 1. Based on the previously observed  $t_{1/2}$  life of this agent, samples will be collected after a single dose of INCB007839 for up to 48 hours post-administration, on Days 1 and 2 of Course 1. Thus, the second dose of INCB007839 scheduled on Day 1 and the two doses scheduled on Day 2 will be held. Because the drug administration along with food will likely increase the inter-patient variability in the absorption process, the drug should be taken as much as possible without food (1 hour before or 2 hours after meals). Because it was shown in adults that the single-dose pharmacokinetic profile was able to accurately predict the steady-state pharmacokinetic profile, no other required pharmacokinetic samples will be collected in this study beyond 48 hours after the first dose. Cerebrospinal fluid collection is optional.

### 2.4.2 Rationale for Other Correlative Studies

#### 2.4.2.1 *Hypothesis*

Neuroligin-3 cleavage and secretion will be blocked with the use of INCB007839; we hypothesize that it is feasible to measure this in cerebrospinal fluid (CSF) samples from patients. HER2 and HER2 extracellular domain are also blocked; we hypothesize it is feasible to follow these in serum to monitor ADAM10 inhibitor pharmacodynamics. We will explore changes in these parameters with toxicity and outcome to determine if these may correlate with anti-tumor effects.

#### 2.4.2.2 *Preclinical and Clinical Data*

Sources of NLGN3 include both normal brain and the glioma itself. NLGN3 expression in glioma cells is regulated by NLGN3 exposure and shedding is also mediated by ADAM10. ADAM10 inhibition should block neuroligin-3 cleavage and secretion from both normal brain and from glioma cells based on preclinical data as stated above and as published. Changes in NLGN3 secretion may be measurable in CSF samples. Optional CSF samples would allow researchers to monitor this exploratory measure as a potential pharmacodynamic biomarker.

HER2 cleavage is mediated by ADAM10, and serum levels of the HER2 extracellular domain have been found to reflect ADAM10 inhibition. We will therefore test HER2 extracellular domain serum levels at Day 1 pre-dose and at Day 14 ± 2 days of Course 1.

### 3.0 PATIENT SELECTION

**All subjects must meet the following inclusion and exclusion criteria.** No exceptions will be given. Imaging studies to establish eligibility must be done within 3 weeks prior to enrollment. All other clinical evaluations to establish eligibility must be done within 7 days prior to enrollment.

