### 3.1.5 Measurable disease

Patients must have measurable disease in two dimensions on MRI to be eligible (as defined within the protocol, [Section 12.1.2](#)).

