## 3.2 Exclusion Criteria

### 3.2.1 Pregnancy or Breast-feeding

Pregnant women or nursing mothers are excluded from this study. Female patients of childbearing potential must have a negative serum or urine pregnancy test within 72 hours prior to receiving the first dose of study medication. If the urine test is positive or cannot be confirmed as negative, a serum pregnancy test will be required.

- Pregnant or breast-feeding women are excluded from this study due to risks of fetal and teratogenic adverse events as seen in animal studies.

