### 3.2.7 Thrombosis Risk

- Patients with a known coagulopathy or bleeding disorder (e.g., von Willebrand's disease) are not eligible.
- Patients with a history of non-central line related thrombosis or disorders that promote clotting (e.g., anti-thrombin III deficiency, Lupus anticoagulant) are not eligible.
- Significant family history of thrombosis (i.e., deep venous thrombosis or pulmonary embolus) in a first-degree relatives (i.e., parents or siblings) are not eligible.
- Estrogen containing contraceptives are not permitted due to thrombotic risk. Progestin -only contraception along with alternate forms of contraception are acceptable.
- Patients should be counseled to avoid smoking/tobacco products.
- If there is any contraindication to DVT prophylaxis, the patient is not eligible.

Family history must be documented to the best extent it is known.

- 3.2.8 Subjects with current or prior symptomatic intratumoral or intracranial hemorrhage are ineligible.
- 3.2.9 Subjects with asymptomatic evidence of new CNS hemorrhage of more than punctate size (i.e.,  $\geq 4$  mm) and/or more than one punctate focus of hemorrhage ( $< 4$  mm or not seen on more than one slice) on baseline MRI obtained within 14 days prior to study enrollment are ineligible.

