### 3.4 Treatment at the Primary Institution

All experimental protocol therapy should be dispensed and all on-treatment imaging studies should be obtained at a PBTC or study-participating institution. Laboratory studies, excluding pharmacokinetic and biologic assays, may be performed at a CLIA certified laboratory of the investigator's choice with the exception of the dose finding period. Imaging utilized to determine eligibility may be performed at an outside institution if all required imaging sequences are included and the study is deemed of adequate quality by the treating team. All required physical examinations, laboratory parameters need to be performed at the primary PBTC or study-participating institution during the dose finding period of the protocol.

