### 3.5 Criteria to Start Treatment

- Subjects must start therapy within 7 days of enrollment.
- Laboratory values must be no older than 7 days prior to the start of therapy. If a test that is repeated post-enrollment and prior to the start of therapy is outside the limits for eligibility, it must be rechecked within 48 hours prior to the start of therapy. If rechecks are still outside the limits for eligibility, the patient may not receive protocol therapy and will be considered off study.
- If, in the opinion of the treating physician, a patient's neurologic condition significantly worsens within 72 hours prior to treatment, the patient should not start treatment and should be taken off study.

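### Do the 3-week imaging window in section 3.0 and the 14-day MRI window in criterion 3.2.9 leave a gap in the hemorrhage screen?

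*Combined protocol and SAP*

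**What the plan says.** Section 3.0 gives two defaults, both counted back from enrollment. Other clinical evaluations have 7 days. For scans, "Imaging studies to establish eligibility must be done within 3 weeks prior to enrollment". The same section makes every inclusion and exclusion criterion binding, without exceptions.

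Three criteria bear on the MRI and on bleeding:

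- 3.1.5, with no window of its own: "Patients must have measurable disease in two dimensions on MRI to be eligible".
- 3.2.8, also without a window: "Subjects with current or prior symptomatic intratumoral or intracranial hemorrhage are ineligible".
- 3.2.9, which covers asymptomatic new hemorrhage above stated size or number limits: such patients "on baseline MRI obtained within 14 days prior to study enrollment are ineligible".

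A clause in 3.2.7 applies whatever the scan date: "If there is any contraindication to DVT prophylaxis, the patient is not eligible".

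The other places that mention baseline imaging give no age in days. Section 3.4 says "Imaging utilized to determine eligibility may be performed at an outside institution if all required imaging sequences are included", with a further condition on quality. Section 5.4 places the first MRI before therapy, and footnote F of the calendar in section 11 refers back to 5.4. On timing after enrollment, 3.5 says "Subjects must start therapy within 7 days of enrollment". It has a recheck rule for laboratory tests but none for imaging.

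**The concern.** A reader who sets 3.0 beside 3.2.9 finds two ages for what is usually the same baseline MRI. The wording of 3.2.9 adds to the doubt. The pregnancy criterion in 3.2.1 is a plain obligation: patients "must have a negative serum or urine pregnancy test within 72 hours prior to receiving the first dose of study medication". Criterion 3.2.9 instead disqualifies a finding on a scan of a certain age and does not say what happens if no such scan exists. Taken word by word, a patient whose only MRI is 15 to 21 days old could use it for measurable disease under 3.1.5, while a bleed on that scan, or one that arose after it, would escape 3.2.9.

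The stake is safety at entry. Section 6.1 requires low molecular weight heparin throughout treatment, and 3.2.9 is the only criterion that expressly screens imaging for silent bleeding. The 72-hour neurologic check in 3.5 cannot see an asymptomatic bleed. If sites read the text differently, one might enroll on an 18-day-old scan where another would repeat it.

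**Working it through.** The plan gives no figure of its own to reproduce. The check is day arithmetic followed by a comparison of sections.

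**Inputs**

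| Item | Section | Window | Counted back from |
|---|---|---|---|
| Eligibility imaging, default | 3.0 | 3 weeks = 21 days | enrollment |
| Other evaluations, default | 3.0 | 7 days | enrollment |
| MRI for asymptomatic hemorrhage | 3.2.9 | 14 days | enrollment |
| Pregnancy test | 3.2.1 | 72 / 24 = 3 days | first dose |
| Performance status | 3.1.8 | 2 weeks = 14 days | enrollment |
| Enrollment to start of therapy | 3.5 | up to 7 days | n/a |

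**Step 1: are the windows in conflict?** Days 0-14 lie wholly inside days 0-21, so any scan that meets 3.2.9 also meets 3.0. The windows differ only for scans 15 to 21 days old: 21 - 14 = 7 days.

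**Step 2: oldest scan at first dose.**

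- Hemorrhage scan if 3.2.9 governs it: 14 + 7 = 21 days.
- Hemorrhage scan if 3.0 governed it instead: 21 + 7 = 28 days.

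The 28-day figure applies to the bleeding screen only on the second reading.

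**Step 3: which reading fits the rest of section 3?** Two other criteria carry their own windows beside the 7-day default. The pregnancy test is tighter (3 days, from first dose). Performance status is looser (14 days against 7). If the defaults in 3.0 overrode the individual criteria, the 2 weeks in 3.1.8 would have no effect, and neither would the 14 days in 3.2.9. The text is coherent only if 3.0 supplies defaults and a criterion's own window replaces them. On that reading the 14-day window governs 3.2.9, and the 21-day window serves criteria without their own, such as 3.1.5.

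**Step 4: is a scan of that age needed?** Section 4.3.1 tells site staff to confirm, before registration, that each criterion is met within its stated time limit. Section 13.3 requires upload of the source documents that support eligibility. With 3.0 allowing no exceptions, a site cannot confirm or document 3.2.9 without an MRI at most 14 days old. The duty is there by implication.

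**Step 5: the patient with only a 15-21 day scan.**

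- On the natural reading, the MRI is repeated before enrollment.
- On the literal reading, it is not, and the last look for silent bleeding is up to 7 days older than 3.2.9 describes.
- If the older scan already shows a bleed, the 3.2.7 clause on contraindications to prophylaxis still applies on either reading.

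**The case for a change.** The strongest case for acting is that an implied duty is weaker than a stated one in a safety criterion. The protocol has no rule of precedence between 3.0 and the individual criteria. The specific windows run in both directions from the defaults, so a site cannot simply assume that the stricter one wins. Criterion 3.2.1 shows that the drafters knew how to write an obligation. The 3.2.7 clause rests on judgment, whereas 3.2.9 sets limits on size and number. A wording amendment would be cheap.

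Part of this stands: nowhere is a 14-day MRI ordered in a sentence of its own, and a cross-reference would make the text easier to follow.

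The rest carries less weight. Windows that run both ways support the view that each criterion's own window replaces the default; the stricter-wins principle is not needed. The difference in form from 3.2.1 is one of drafting style: 3.2.9 names a baseline MRI obtained within its window and so takes for granted that there is one, and 3.1.8 attaches its window in the same manner. The worst case needs a site to see a disqualifying bleed, set it aside because the scan is too old, and then judge heparin prophylaxis not to be contraindicated. Nor would a repeat MRI for an older scan be a cost of rewording, since 3.2.9 on its natural reading already calls for it.

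**Conclusion.** No change to the plan follows. The two windows are nested, and a site that applies each criterion with its own time limit, as 4.3.1 asks, obtains an MRI within 14 days for 3.2.9 and may rely on the 21-day default where no other window is given. The remaining point is editorial.

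Its size is a 7-day band of scan ages, and a last MRI at most 21 days old at first dose on the natural reading, against 28 on the literal one. How many patients fall in the band cannot be estimated, because the documents give no scan ages. The dose-finding rules, sample size and analyses in section 9 do not use scan age.

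The conclusion assumes that sites follow the registration check in 4.3.1 and treat criterion-specific windows as replacing the defaults. It takes no view on whether 14 or 21 days is the better clinical window.

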#### 3.1 Inclusion Criteria

##### 3.1.1 Histological Diagnosis

- Patients with recurrent/progressive high-grade gliomas, as defined by progressive neurologic abnormalities or worsening neurologic status not explained by causes unrelated to tumor progression (e.g., anticonvulsant or corticosteroid wean, electrolyte disturbances, sepsis, hyperglycemia, etc.), **OR** a  $\geq 25\%$  increase in the bi-dimensional measurement, taking as a reference the smallest disease measurement recorded since diagnosis utilizing the MRI sequence best demonstrating tumor, **OR** the appearance of a new/metastatic tumor lesion(s) since diagnosis.
- Eligible diagnoses include but are not limited to the following: diffuse intrinsic pontine glioma (DIPG), H3K27M-altered diffuse midline glioma (DMG), glioblastoma multiforme, anaplastic astrocytoma and anaplastic oligodendrogloma. Spinal cord tumors are eligible with pathologic confirmation of the above.

- Please note: Patients with a radiographically typical DIPG at diagnosis, defined as a tumor with a pontine epicenter and diffuse involvement of more than 2/3 of the pons, are eligible without histologic confirmation.
- Patients with pontine lesions that do not meet these radiographic criteria will be eligible if there is histologic confirmation of pontine glioma WHO II-IV.
- Patients with diffuse or multi-focal disease are eligible; patients with leptomeningeal spread are eligible.

### 3.1.2 Age

Patients must be  $\geq 3$  but  $\leq 21$  years of age at the time of enrollment.

### 3.1.3 BSA

- Patients must have a BSA  $\geq 0.70-2.50 \text{ m}^2$  for dose  $120 \text{ mg/m}^2/\text{dose BID}$ .
- Patients must have a BSA  $\geq 0.55-2.80 \text{ m}^2$  for dose  $80 \text{ mg/m}^2/\text{dose BID}$  (patients who have BSA  $0.55-1.00 \text{ m}^2$  will only receive  $100 \text{ mg AM dose}$ ).

### 3.1.4 Ability to Swallow

Patients must be able to swallow tablets whole.

### 3.1.5 Measurable disease

Patients must have measurable disease in two dimensions on MRI to be eligible (as defined within the protocol, [Section 12.1.2](#)).

### 3.1.6 Prior Therapy

- Patients must have failed at least 1 standard, tumor-directed treatment besides surgery and recovered from the acute treatment-related toxicities (defined as  $<$  Grade 1) of all prior chemotherapy, immunotherapy, or radiotherapy prior to enrollment on this study.
- Patients must be  $\geq 28$  days from any prior surgery at the time of study enrollment (with the exception of minor dental and dermatological procedures).

#### 3.1.6.1 *Chemotherapy*

Patients must have received their last dose of known myelosuppressive anticancer therapy at least 21 days prior to enrollment or at least 42 days if nitrosourea.

#### 3.1.6.2 *Investigational/Biologic Agent*

- Biologic or investigational agent (anti-neoplastic):

Patients must have recovered from any acute toxicity potentially related to the agent and received their last dose of the investigational or biologic agent  $\geq 7$  days prior to study enrollment.

- For agents that have known adverse events occurring beyond 7 days after administration, this period must be extended beyond the time during which adverse events are known to occur.

- Monoclonal antibody treatment and agents with known prolonged half-lives:

Patients must have recovered from any acute toxicity potentially related to the agent and received their last dose of the agent  $\geq 28$  days prior to study enrollment.

- Immunotherapies:

Patients who have received checkpoint inhibitors or other immunotherapies with a known potential for pseudoprogression and who have assumed tumor progression must be at least 12 weeks from prior immunotherapy **AND** have at least two MRI scans at least 4 weeks apart demonstrating further progression **OR** have a biopsy to confirm tumor progression **OR** have new site(s) of disease.

#### 3.1.6.3 *Radiation*

Patients must have had their last fraction of:

- Craniospinal irradiation, whole brain radiation, total body irradiation or radiation to  $\geq 50\%$  of pelvis or spine  $\geq 42$  days prior to enrollment.
- Focal irradiation  $\geq 14$  days prior to enrollment.
- Local palliative irradiation to site other than primary tumor progression site  $\geq 14$  days prior to enrollment.

#### 3.1.6.4 *Stem Cell Transplant*

Patients must be:

- $\geq 6$  months since allogeneic stem cell transplant prior to enrollment with no evidence of active graft vs. host disease.
- $\geq 3$  months since autologous stem cell transplant prior to enrollment.

#### 3.1.7 Neurologic Status

- Patients with neurological deficits should have deficits that are stable for a minimum of 7 days prior to enrollment.
- Patients with seizure disorders may be enrolled if seizures are well controlled.

#### 3.1.8 Performance Status

Karnofsky Performance Scale (KPS for  $> 16$  years of age) or Lansky Performance Score (LPS for  $\leq 16$  years of age) assessed within 2 weeks of enrollment must be  $\geq 60$ , including ability to ambulate with or without assistance.

#### 3.1.9 Organ Function

Patients must have adequate organ and marrow function as defined below:

- Absolute neutrophil count  $\geq 1.0 \times 10^9$  cells/L
- Platelets  $> 100 \times 10^9$  cells/L (unsupported, defined as no platelet transfusion within 7 days)
- Hemoglobin  $\geq 8$  g/dL (may receive transfusions)
- Total bilirubin  $\leq 1.5$  times institutional upper limit of normal (ULN)
- ALT (SGPT) and AST (SGOT)  $< 3 \times$  institutional upper limit of normal (ULN)
- Albumin  $\geq 2$  g/dL
- Serum creatinine based on age/gender as noted in Table 1. Patients that do not meet the criteria in Table 1 but have a 24-hour Creatinine Clearance or GFR (radioisotope or iothalamate)  $\geq 70$  mL/min/1.73 m^2 are eligible.

**Table 1: Serum Creatinine for age/gender**

Age	Maximum Serum Creatinine (mg/dL)	
	Male	Female
3 to < 6 years	0.8	0.8
6 to < 10 years	1	1
10 to < 13 years	1.2	1.2
13 to < 16 years	1.5	1.4
≥ 16 years	1.7	1.4

The threshold creatinine values in this Table were derived from the Schwartz formula for estimating GFR (Schwartz et al. J. Peds, 106:522, 1985) utilizing child length and stature data published by the CDC.

### 3.1.10 Corticosteroids

Patients who are receiving dexamethasone must be on a stable or decreasing dose for at least 7 days prior to enrollment.

### 3.1.11 Growth Factors

Patients must be off all colony-forming growth factor(s) for at least 7 days prior to enrollment (e.g., filgrastim, sargramostim, or erythropoietin). Fourteen (14) days must have elapsed if patient received a long-acting formulation.

### 3.1.12 Pregnancy Prevention

Patients of childbearing or child fathering potential must be willing to use a medically acceptable form of birth control, which includes abstinence, while being treated on this study.

### 3.1.13 Informed Consent

The patient or parent/guardian is able to understand the consent and is willing to sign a written informed consent document according to institutional guidelines.

### 3.1.14 HIV Positive Patients

HIV-positive patients are eligible if the following criteria are met:

- Stable on their antiretroviral agents
- Have CD4 counts above 400/mm^3
- Undetectable viral loads, and
- No need for prophylactic medications for an opportunistic infections

## 3.2 Exclusion Criteria

### 3.2.1 Pregnancy or Breast-feeding

Pregnant women or nursing mothers are excluded from this study. Female patients of childbearing potential must have a negative serum or urine pregnancy test within 72 hours prior to receiving the first dose of study medication. If the urine test is positive or cannot be confirmed as negative, a serum pregnancy test will be required.

- Pregnant or breast-feeding women are excluded from this study due to risks of fetal and teratogenic adverse events as seen in animal studies.

